- a) All scheduled visits will have a window of  $\pm 3$  days unless otherwise stated, all procedures to be completed  $\leq 3$  days prior to commencing subsequent treatment cycle
- b) Does not need to be repeated on Cycle 1, Day 1, if completed  $\leq 14$  days prior to registration
- c) To include blood pressure, pulse rate, temperature, weight. Screening for second primary malignancies and especially dermatologic cancers is recommended per standard clinical practice. All patients must have documentation at baseline for any skin lesions considered at risk of a melanoma or non-melanomatous skin cancer. If any such lesion is identified, it should be addressed immediately. During the conduct of the clinical trial, please monitor for any potential skin malignancy lesions, as considered clinically necessary. All male patients at risk for prostate cancer recommended to undergo screening including a serum PSA level if not done  $\leq 6$  months prior to registration.
- d) Hematology: CBC with differential, including hemoglobin and platelet count
- e) Coagulation: prothrombin time (PT) and international normalized ratio (INR)
- f) Blood chemistries: sodium, chloride, potassium, magnesium, phosphate, uric acid, BUN, glucose, ALT/AST (SGPT/SGOT), alkaline phosphatase, total protein, total bilirubin, albumin, serum creatinine, and estimated creatinine clearance (Appendix V), calcium and lactate dehydrogenase (LDH).
- g) Standard of care procedure  $\leq 28$  days prior to registration, and to document CR, sCR or PD while on treatment (whether PD noted to single-agent ibr or the combination of ibr with len+dex). **NOTE:** For Phase II, an additional bone marrow biopsy and aspirate will be collected after completion of Cycle 1 of treatment for correlative sample collection in order to evaluate the exploratory endpoints of the study.
- h) Skeletal bone survey and PET scan for extramedullary disease assessment  $\leq 28$  days prior to registration and then at any time when disease progression is noted, clinically or on laboratory assessment.
- i) Per Section 14, to coincide with the timing of all standard-of-care bone marrow aspirate/biopsy collections in addition to a mandatory collection done prior to starting second cycle in Phase 2.

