7.3 Phase I – determination of Maximum Tolerated Dose (MTD)

7.31 Dose Escalation (Phase I):

Dose level escalations/de-escalations will be done during the Phase I portion for Ibrutinib. In case any dose modifications to ibrutinib and/or dexamethasone are required during the Phase I portion due to specific adverse events requiring dose modifications (as outlined in Section 8 below), a specific discussion should be done with the study PI and appropriately documented. A patient on the Phase I portion of the study who develops a DLT should have treatment omitted until the toxicity resolves to Grade 1 or better or baseline, and then may be restarted at the next lower dose level for the DLT portion only. .

Only DLTs occurring in the first cycle and at the patient's first Dose Level of treatment will be used to guide dose determination for the Phase II portion of the trial per Section 16.22.

Dose level	Ibrutinib	Lenalidomide	Dexamethasone**
-1	280 mg	25 mg	40 mg
1*	420 mg	25 mg	40 mg
2	560 mg	25 mg	40 mg
3	700 mg	25 mg	40 mg
4	840 mg	25 mg	40 mg

\*Starting dose level

\*\*Starting dose level of dexamethasone for patients  $\geq 75$  years old will be 20mg

7.311 Three patients will be treated at each dose level and observed for a minimum of 28 days, to assess toxicities, before new patients are treated. Doses will not be escalated in any individual patient.

7.312 Investigators are to contact the Study Chair as soon as any dose-limiting toxicity (DLT) occurs.

7.32 **Definitions of DLT:** For this protocol, dose-limiting toxicity (DLT) will be defined as an adverse event attributed (definitely, probably, or possibly) in the first cycle to the study treatment and meeting the following criteria (as per CTCAE V4.0):

- Any Grade 3 or greater non-hematological toxicity will be a DLT, with the exception of: fatigue, inadequately treated nausea, vomiting, or diarrhea; inadequately treated hyperglycemia; or hypersensitivity reaction. A rash considered associated with immune activation phenomenon secondary to

lenalidomide and/or ibrutinib will not be considered a DLT and may be treated concurrent to study treatment with solumedrol (Recommended treatment would be with a Medrol Dose Pak®) For a baseline abnormality prior to drug therapy, a worsening by at least 2 CTCAE grades and of clinical significance will be considered a DLT.

- b) Grade 3 nausea, vomiting or diarrhea will be a DLT if it occurs despite appropriate maximal anti-emetic and/or antidiarrheal therapy.

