- c) Grade 3 hyperglycemia will be a DLT if the patient is symptomatic or glucose level is  $>300$  mg/ml despite appropriate administration of insulin and/or oral antidiabetic agents.
- d) Grade 4 neutrophil count decreased lasting  $>7$  days or Grade 3 or 4 febrile neutropenia associated with fever ( $\geq 38.5^{\circ}\text{C}$ ).
- e) Grade 4 platelet count decreased. Grade 3 platelet count decreased lasting  $>7$  days or associated with Grade 2 or higher hemorrhage.
- f) Delay of treatment with ANY agent for  $\geq 14$  days due to possibly, probably or definitely treatment-related toxicity during Cycle 1.

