### 8.0 Dosage Modification Based on Adverse Events

Strictly follow the modifications in this table for the first cycle of combination treatment with ibrutinib, lenalidomide and dexamethasone, until individual treatment tolerance can be ascertained (**not including the treatment period where MTD of the combination is being determined as per Section 7.31**). Thereafter, these modifications should be regarded as guidelines to produce mild-to-moderate, but not debilitating, side effects. Reductions apply to treatment given in the preceding cycle and are based on adverse events observed since the prior dose.

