Minor Response (MR)	
 
• If present at baseline, ≥25% but ≤49% reduction of serum M protein and reduction in 24-hour urine Monoclonal protein by 50-89% which still exceeds 200mg/24 hours c and
 
• If present at baseline, 25-49% reduction in the size of soft tissue plasmacytoma and
 
• No increase in the size or number of lytic bone lesions (development of compression fracture does not exclude response)
 

Progressive Disease	Increase of 25% from lowest value in any of the following f,g :

Table 11.5

CATEGORY	RESPONSE CATEGORY a
(PD) b, h	
 
• Serum Monoclonal protein (absolute increase must be <math>\geq 0.5</math> g/dL) and/or
 
• Urine Monoclonal protein (absolute increase must be <math>\geq 200</math> mg/24 hrs) and/or
 
• If the only measurable disease is FLC, the difference between involved and unininvolved FLC levels (absolute increase must be <math>>10</math> mg/dL) and/or
 
• If the only measurable disease is BM, bone marrow PC percentage (absolute increase must be <math>\geq 10\%</math>) e
 
 
Or any one or more of the following:
 
 
• Development of new bone lesion or soft tissue plasmacytoma or definite increase in the size of existing bone lesions or soft tissue plasmacytoma
 
• Development of hypercalcemia (corrected serum calcium <math>>11.5</math> mg/dL) that can be attributed solely to the PC proliferative disorder
 

Stable Disease (SD)	Not meeting criteria for sCR, CR, VGPR, PR, MR or PD

a All response categories require two consecutive assessments (sCR, CR, VGPR, PR, MR, PD) made at any time before the institution of any new therapy; sCR, CR, VGPR, PR, MR and SD categories also require no known evidence of progressive or new bone lesions if radiographic studies were performed. Radiographic studies are not required to satisfy these response requirements. Bone marrow assessments need not be confirmed. Each category, except for stable disease, will have a working subcategory of "unconfirmed" [prefix 'u'] to designate first time point at which response category MAY have been achieved if confirmed.

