### **Appendix XI Serum Calcium Corrected for Albumin**

If calcium is expressed in mg/dL and albumin is expressed in g/dL:

$$\text{Corrected calcium (mg/dL)} = \text{serum calcium (mg/dL)} + 0.8 \times (4 - \text{serum albumin [g/dL]})$$

If calcium is expressed in mmol/L and albumin is expressed in g/L:

$$\text{Corrected calcium (mmol/L)} = \text{serum calcium (mmol/L)} + 0.02 \times (40 - \text{serum albumin [g/L]})$$

Source: Burtis 1999

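### The glucose limit in DLT item 7.32(c) is printed as more than 300 mg/ml (30,000 mg/dL), so the laboratory part of that item can never be met

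*Combined protocol and SAP*

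**What the plan says.** Two criteria in Section 7.32 bear on hyperglycemia.

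- The first criterion (item a) is the general rule: "Any Grade 3 or greater non-hematological toxicity will be a DLT, with the exception of" a short list. That list includes "inadequately treated hyperglycemia; or hypersensitivity reaction".
- Item (c) is the specific rule: "Grade 3 hyperglycemia will be a DLT if the patient is symptomatic or glucose level is" above 300 "mg/ml despite appropriate administration of insulin and/or oral antidiabetic agents".

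Item (c) therefore has two limbs joined by an or: a clinical one (symptoms) and a laboratory one (a glucose value that persists on treatment). The laboratory limb contains the only numeric glucose limit in the protocol.

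DLTs in Cycle 1 are the events counted in Sections 16.21 to 16.224. No DLT in 3 patients allows escalation. One in 3 leads to expansion to 6. Two or more mean that the MTD has been exceeded.

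**The concern.** A blood glucose of 300 mg per millilitre is not possible, so one of the two limbs of item (c) is dead as printed. The patient it was evidently written for is one with Grade 3 hyperglycemia on treatment, without symptoms, whose glucose stays above the limit. Under item (c) as printed, that patient is not counted.

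The place matters more than the slip. This is a threshold in the operative DLT definition, and a single DLT can change a cohort's decision. The criterion is also relevant to the regimen: Section 15.27 lists hyperglycemia among the lenalidomide toxicities seen in more than 10% of patients, and Section 15.37 warns that dexamethasone can worsen diabetes.

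**Working it through.** **The plan's own figures.** The protocol gives no derivation for the glucose limit, so there is nothing to reproduce for it. The table that uses DLT counts, in 16.227, can be checked. With true DLT rate p, the probability of escalating is

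P = (1−p)³ + 3p(1−p)² × (1−p)³

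| p | Computed | Printed in 16.227 |
|---|---|---|
| 0.10 | 0.906 | 0.91 |
| 0.20 | 0.709 | 0.71 |
| 0.30 | 0.494 | 0.49 |
| 0.40 | 0.309 | 0.31 |
| 0.50 | 0.172 | 0.17 |

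The table is correct. It depends only on p, so the unit error does not change it.

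**Unit conversion.** The inputs are the limit of 300 mg/ml from 7.32(c), 1 dL = 100 mL, and the reference albumin of 4 g/dL in the Appendix XI formula, used only for scale.

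- As printed: 300 mg/mL × 100 mL/dL = 30,000 mg/dL = 30 g/dL.
- Against reference albumin: 30 / 4 = 7.5 times.
- If mg/dL was meant: 300 mg/dL = 3 mg/mL = 0.3 g/dL.
- Ratio of printed to likely intended limit: 30 / 0.3 = 100.

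**Units elsewhere.** Section 11.1 gives involved free light chain per dL, Appendix V gives creatinine in mg/dL, and Table 11.5 gives corrected calcium in mg/dL. Appendix XI begins "If calcium is expressed in mg/dL and albumin is expressed in g/dL". Where SI alternatives appear (Appendices XI and XII), they are per litre. The unit mg/mL is used in 15.32 for the strength of oral dexamethasone solutions, which is not a blood level.

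**Is the limit given correctly somewhere else?** It is not.

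- Section 4.1, footnote f, lists "sodium, chloride, potassium, magnesium, phosphate, uric acid, BUN, glucose" and further analytes, with no unit or limit for glucose.
- The hyperglycemia row in Section 8.4 works by CTCAE grade only.
- Section 8.0 applies its table strictly in the first combination cycle, but "not including the treatment period where MTD of the combination is being determined as per Section 7.31".

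**Which patients are affected?** Take Grade 3 hyperglycemia, at least possibly related to treatment, in Cycle 1, adequately treated, with glucose above 300 mg/dL.

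| Patient | Item (a), read literally | Item (c) as printed | Item (c) in mg/dL |
|---|---|---|---|
| Symptomatic | DLT | DLT | DLT |
| Asymptomatic | DLT | not met | DLT |

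Only the asymptomatic row changes. It affects the DLT count only if item (c) is applied as the specific rule that displaces item (a). The wording of (c) says that the event counts if its condition holds, not only if, so an unmet limb in (c) does not cancel (a).

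**The case against.** The strongest reply is that nothing in the dose-finding is shown to move. Item (a) exempts only hyperglycemia that has not been adequately treated, while the faulty limb concerns hyperglycemia that persists on treatment. Read literally, (a) already catches every event that the limb would catch. There are other safeguards. The symptomatic limb still works. Section 7.31 sends Phase I changes to ibrutinib or dexamethasone to a documented discussion with the study PI. Section 8.4 stops dexamethasone for Grade 3 or 4 hyperglycemia despite adequate management. Item (f) makes a treatment-related delay of 14 days or more in Cycle 1 a DLT. Section 16.52 has adverse events from all cycles reviewed. An impossible limit also invites readers to correct it themselves. Finally, the doubt is over one letter, and other spellings in the text are faulty.

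Most of this stands as an argument about size: it makes the practical effect probably small and rules out calling this a flaw in the escalation rule. It does not repair item (c). Item (a) contains no glucose value. Item (c), like item (b) for nausea, vomiting and diarrhea, sets out when an exempted toxicity does count, so a site could reasonably treat it as the governing rule. Discussion with the PI and later review are not the same as a counted DLT, and whether stopping dexamethasone is a delay under item (f) is open to argument. On the spelling, the sentence is complete prose with no sign of damage at that point.

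**Conclusion.** The point holds. The limit in 7.32(c) is wrong as written: 30,000 mg/dL as printed, against 300 mg/dL if mg/dL was intended, a factor of 100. The laboratory limb cannot be met, and (c) reduces to symptomatic Grade 3 hyperglycemia.

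This is a low-priority correction. Sample size, significance level, power and the 16.227 table are unaffected. No effect on escalation is claimed, because the documents give no frequency for Grade 3 hyperglycemia and item (a) probably captures the same events.

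Two assumptions remain. One is that mg/dL was the intended unit, which the units used for other serum values support but no text states. The other is that 300 was the intended number, which only the study team can confirm.

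**What to change.** In 7.32(c), change mg/ml to mg/dL, and have the study chair confirm that 300 is the intended limit. This is a one-word change with no effect on the design, the sample size or data collection. It could be made with a protocol amendment; the document history lists Amendment 4 as pending approval. How items (a) and (c) should fit together is the sponsor's choice and is not needed for this correction.

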#### 7.4 Overdose

Any dose of study drug in excess of that specified in this protocol is considered to be an overdose. Signs and symptoms of an overdose that meet any Serious Adverse Event criterion must be reported as a Serious Adverse Event in the appropriate time frame and documented as clinical sequelae to an overdose.

There is no specific experience in the management of ibrutinib overdose in patients. No maximum tolerated dose (MTD) was reached in the Phase 1 study in which subjects received up to 12.5 mg/kg/day (1400 mg/day). Healthy subjects were exposed up to single dose of 1680 mg. One healthy subject experienced reversible Grade 4 hepatic enzyme increases (AST and ALT) after a dose of 1680 mg. Subjects who ingested more than the recommended dosage should be closely monitored and given appropriate supportive treatment.

Refer to Section 10 for further information regarding AE reporting.

### 8.0 Dosage Modification Based on Adverse Events

Strictly follow the modifications in this table for the first cycle of combination treatment with ibrutinib, lenalidomide and dexamethasone, until individual treatment tolerance can be ascertained (**not including the treatment period where MTD of the combination is being determined as per Section 7.31**). Thereafter, these modifications should be regarded as guidelines to produce mild-to-moderate, but not debilitating, side effects. Reductions apply to treatment given in the preceding cycle and are based on adverse events observed since the prior dose.

**ALERT:** **ADR reporting may be required for some adverse events (See Section 10)**

#### 8.1 General Considerations:

- a) Missed doses are to be omitted rather than made up, unless the dose of one of the study drugs was forgotten and remembered on the same day, in which case the dose can be taken that day. Any doses missed on a particular day are not to be made up the next day.

Doses that are considered to be vomited are not to be made up and a mention about the time of dose and time of vomiting episode should be made in the pill diary.

- b) If multiple toxicities are experienced, dose modifications will be based on the toxicity requiring the largest dose reduction.
- c) Reductions are based on the dose given in the preceding cycle and are based on toxicities with an attribution of possible, probable, or definite that were observed since the prior toxicity evaluation.
- d) If either ibrutinib or lenalidomide must be permanently discontinued, the patient will be removed from the protocol therapy.
- e) If a drug is omitted due to specific adverse events and the patient is on combination therapy, the other agents, considered unrelated to the adverse event may be continued.
- f) A dose omission of >28 days for ibrutinib or lenalidomide is not allowed. If a patient cannot be administered a dose for >28 days due to adverse events or any other reason, the patient should be removed from the study treatment and go to event monitoring.
- g) Patients will be removed from the study if we are unable to manage the adverse events they experience, and it is therefore necessary to permanently discontinue ibrutinib or lenalidomide. These events are listed in the tables in Section 8.3 and 8.5.

8.2 Dose Reductions for Phase I cycles 2 and beyond and Phase II portion (based on Adverse Events in Tables below):

8.21 The following recommended dose modifications will be utilized for ibrutinib, lenalidomide and/or dexamethasone separately as per the best judgment of which drug was most likely to have caused the toxicity:

8.22 Dose level tables

8.221 Lenalidomide

Dose Level	Lenalidomide* Starting Dose 25 mg
1st dose reduction	20 mg
2nd dose reduction	15 mg
3rd dose reduction	10 mg
4 th dose reduction	Discontinue

\*Other than lenalidomide dose adjusted for renal dysfunction

8.222 Dexamethasone

Dose Level	Dexamethasone Starting Dose 40 mg*
1st dose reduction	20 mg
2nd dose reduction	12 mg
3rd dose reduction	8 mg
4th dose reduction	Discontinue

\*Starting dose level of dexamethasone for patients  $\geq 75$  years old will be 20mg so those patients will start with the 2nd dose reduction row.

## 8.223 Ibrutinib

Ibrutinib	Starting Dose 840 mg	Starting Dose 700 mg	Starting Dose 560 mg	Starting Dose 420 mg	Starting Dose 280 mg
1 st dose reduction	700 mg	560 mg	420 mg	280 mg	Discontinue
2 nd dose reduction	560 mg	420 mg	280mg	Discontinue	
3 rd dose reduction	420 mg	280mg	Discontinue		
4 th dose reduction	280 mg	Discontinue			
5 th dose reduction	Discontinue				

## 8.3 Lenalidomide Dose Modifications

→ → Use the NCI Common Terminology Criteria for Adverse Events (CTCAE) version 4.0\*  
unless otherwise specified ← ←

CTCAE System/Organ/Class (SOC)	ADVERSE EVENT	AGENT	ACTION**
Investigations	Platelet count decreased Grade 4	Lenalidomide	
*Omit dose until AE has resolved to Grade 1 or better
 
 
• Follow CBC weekly
 
• If thrombocytopenia <math><30,000/\text{mm}^3</math> recurs, reduce dose by one dose level (by 5 mg) and continue therapy when platelet count <math>\geq 30,000/\text{mm}^3</math>
 
 
If, after lenalidomide has been omitted, and the AE does not return to <math>\leq</math>Grade 1 within 4 weeks, then the patient must be removed from protocol treatment and proceed to Event Monitoring

	Neutrophil count decreased Grade 4		
*Omit dose until AE has resolved to Grade 1 or better
 
 
• Follow CBC weekly
 
* If neutropenia has resolved to <math>\leq</math>Grade 2, resume dose at one level lower
 
*If, after lenalidomide has been omitted, and the AE does not return to <math>\leq</math>Grade 1 within 4 weeks, then the patient must be removed from protocol treatment and proceed to Event Monitoring
 

CTCAE System/Organ/Class (SOC)	ADVERSE EVENT	AGENT	ACTION**
Blood and lymphatic system disorders	Anemia Grade 4		
 
*Omit dose until AE has resolved to Grade 2 or better
 
• Follow CBC weekly
 
* If anemia has resolved to <math>\leq</math>Grade 2, resume dose at one level lower
 
*If, after lenalidomide has been omitted, and the AE does not return to <math>\leq</math>Grade 2 within 4 weeks, then the patient must be removed from protocol treatment and proceed to Event Monitoring
 

	Febrile neutropenia $\geq$ Grade 3		
 
• Omit dose and follow CBC weekly
 
• If neutropenia has resolved to <math>\leq</math>Grade 2, resume dose at same level with GCSF support (See Section 9.7)
 

Cardiac disorders	Sinus bradycardia/other cardiac arrhythmia Grade 2	Lenalidomide	
 
Omit dose and follow at least weekly until resolution
 
• If AE resolves to <math>\leq</math>Grade 1, reduce dose by one dose level (by 5mg) and continue therapy
 

	$\geq$ Grade 3		
 
• Discontinue study treatment and go to event monitoring
 

Vascular disorders	Thromboembolic event $\geq$ Grade 3		
 
• Omit dose and start anticoagulation; restart at investigator's discretion (maintain dose level)
 

Immune system disorders	Allergic reaction Grade 2-3		
 
• Omit dose and follow at least weekly until resolution
 
• If AE resolves to <math>\leq</math>Grade 1, reduce dose by 5 mg and continue therapy
 

	Anaphylaxis Grade 4		
 
• Discontinue study treatment and go to event monitoring
 

Skin and subcutaneous tissue disorders	Erythema multiforme $\geq$ Grade 3		Discontinue study treatment and go to event monitoring
	Skin ulceration $\geq$ Grade 2		Discontinue study treatment and go to event monitoring
	Other: Non-blistering rash Grade 3		
 
• If Grade 3 omit dose and follow weekly until resolution
 
• If AE resolves to <math>\leq</math>Grade 2 continue therapy
 

	Other: Non-blistering rash Grade 4		
 
• Discontinue study treatment and go to event monitoring
 

Other AEs	Non-hematologic AE assessed as related to lenalidomide $\geq$ Grade 3		
 
• Omit dose and follow at least weekly until resolution
 
• If the AE resolves to <math>\leq</math>Grade 2, implement one dose reduction step and continue therapy (per Table 8.2)
 

\* Located at [http://ctep.cancer.gov/protocolDevelopment/electronic\\_applications.ctc.htm](http://ctep.cancer.gov/protocolDevelopment/electronic_applications.ctc.htm)

\*\* Use the following to describe actions in the Action column:

- Omit = The current dose(s) for the specified drug(s) during a cycle is skipped. The patient does not make up the omitted dose(s) at a later time
- Hold/Delay = The current dose(s) of all drugs during a cycle is delayed. The patient does make up the delayed dose(s) when the patient meets the protocol criteria to restart drugs.
- Discontinue = The specified drug(s) are totally stopped.

If lenalidomide has been omitted and the toxicity does not return to  $\leq$ Grade 2 within 28 days, the patient must be removed from protocol treatment and proceed to Event Monitoring.

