## 8.5 Ibrutinib Dose Modifications

→ → Use the NCI Common Terminology Criteria for Adverse Events (CTCAE) version 4.0\* unless otherwise specified ← ←

CTCAE System/Organ/Class (SOC)	ADVERSE EVENT	AGENT	ACTION**
Investigations	Neutrophil count decreased Grade 4 lasting >7 days	Ibrutinib	Omit ibrutinib** until recovery to Grade ≤1 or baseline May restart at same dose for first occurrence Each subsequent occurrence may restart at next lower dose after recovery to Grade ≤1 or baseline If AE occurs at lowest dose discontinue treatment and go to event monitoring
	Platelet count decreased Grade ≥3		
Blood and lymphatic system disorders	Febrile neutropenia ≥Grade 3	Ibrutinib	Omit ibrutinib** until fever resolves and ANC ≥1000/µL, then resume ibrutinib at the previous dose
Gastrointestinal disorders	Nausea ≥Grade 3 (if persistent despite optimal antiemetic therapy) Vomiting ≥Grade 3 (if persistent despite optimal antiemetic therapy) Diarrhea ≥Grade 3 (if persistent despite optimal anti-diarrheal therapy)	Ibrutinib	Omit ibrutinib** until recovery to Grade ≤1 or baseline May restart at same dose for first occurrence Each subsequent occurrence may restart at next lower dose after recovery to Grade ≤1 or baseline If AE occurs at lowest dose discontinue treatment and go to event monitoring
Other (Non-hematologic)****	Any other Grade 4 AE or any unmanageable Grade 3 AE	Ibrutinib	Omit ibrutinib** until recovery to Grade ≤1 or baseline May restart at same dose for first occurrence Each subsequent occurrence may restart at next lower dose after recovery to Grade ≤1 or baseline If AE occurs at lowest dose discontinue treatment and go to event monitoring

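### Phase II patients entering with clinically significant Child-Pugh A impairment start ibrutinib at the phase I dose, not the recommended 280 mg/day (and, a minor point, the Grade 4 neutropenia row in 8.3 contradicts itself on restarting lenalidomide)

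*Combined protocol and SAP*

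**What the plan says.** **Ibrutinib and hepatic impairment.** Exclusion 3.29e1 bars from phase I anyone with active, clinically significant impairment of Child-Pugh class A, B or C. Exclusion 3.29e2 bars only classes B and C from phase II, so class A may enter. Section 7.12 gives all phase II patients the phase I dose level and lists no hepatic exception. Section 15.15(e) recommends 280 mg/day for class A and 140 mg/day for class B. Section 8.51 uses the same two doses, but as reductions for patients whose impairment arises during the study.

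**Lenalidomide after Grade 4 neutropenia.** The row in 8.3 gives three instructions:

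- omission: "Omit dose until AE has resolved to Grade 1 or better" (the platelet row has the same sentence);
- restart, with a ≤ sign before the grade: "Grade 2, resume dose at one level lower";
- removal, if the count is not back to ≤ "Grade 1 within 4 weeks, then the patient must be removed from protocol treatment and proceed to Event Monitoring".

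The protocol uses both grades elsewhere. The Grade 4 anemia row keeps Grade 2 for all three steps, beginning "Omit dose until AE has resolved to Grade 2 or better". The febrile neutropenia row restarts at ≤ "Grade 2, resume dose at same level with GCSF support", and the closing paragraph of 8.3 sets removal at failure to reach ≤ "Grade 2 within 28 days, the patient must be removed from protocol treatment and proceed to Event Monitoring". Against that, the 8.5 row for "Neutrophil count decreased Grade 4 lasting >7 days" has ibrutinib omitted "until recovery to Grade ≤1 or baseline May restart at same dose for first occurrence", and 7.31 asks for Grade 1 or baseline after a DLT.

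Section 8.0 makes the modifications binding only in the first cycle of the three-drug combination, outside the phase I MTD period. After that they are guidelines.

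**The concern.** The hepatic point matters more. A patient who develops class A impairment on treatment has a recommended reduction to 280 mg, while a patient who already has it on day 1 receives the full phase I dose. The second patient belongs to a group that phase I was set up not to test, so the trial will have no tolerability data of its own for that dose in that group. Nothing in the protocol gives the investigator a different starting dose.

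The neutropenia point is a drafting fault. When the count has recovered to Grade 2 and no further, one line says to keep lenalidomide off and another says to restart it one level lower. Two investigators could read the same row and treat the same patient differently.

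**Working it through.** **1. Starting dose against the recommendation.** The possible phase I doses come from the table in 7.31 and the class A recommendation from 15.15(e). The documents do not give the dose that phase I selected, so every level is shown. Ratio = level / 280.

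| Level | Ibrutinib start | Ratio to 280 mg | Excess per day |
|---|---|---|---|
| -1 | 280 mg | 280/280 = 1.0 | 0 mg |
| 1 | 420 mg | 420/280 = 1.5 | 140 mg |
| 2 | 560 mg | 560/280 = 2.0 | 280 mg |
| 3 | 700 mg | 700/280 = 2.5 | 420 mg |
| 4 | 840 mg | 840/280 = 3.0 | 560 mg |

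No level lies below 280 mg, and only level -1 avoids the conflict.

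**2. Can such a patient enter?** Section 3.17 limits bilirubin, AST/ALT and PT/INR but sets no albumin or ascites limit. Under Appendix XII, five measures at 1 point each give 5 points. Four at 1 point and one at 2 points (low albumin or mild ascites, for example) give 4 + 2 = 6 points. Both totals are class A. The laboratory limits therefore narrow the group without emptying it. Because 5 is the lowest possible score, the class alone does not identify liver disease; the words about clinical significance in 3.29e do that.

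**3. Which cycle is binding for lenalidomide?** Phase I cycle 1 falls in the MTD period, which 8.0 carves out. Phase II cycle 1 has no lenalidomide (7.12). The binding cycle is essentially phase II cycle 2, which lasts 28 days with lenalidomide on days 1-21.

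**4. Size of the restart conflict in that cycle.** Let omission start on cycle day s, and let Grade 2 first be seen w days later, with w = 7, 14 or 21 because the row asks for weekly counts. Suppose the patient stays at Grade 2. One reading restarts on day s + w; the other stays off. The differing dosing days left in the cycle number 21 - (s + w) + 1 = 22 - s - w, or 0 if that is negative.

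| w | Formula | s = 1 | s = 8 | s = 15 or later |
|---|---|---|---|---|
| 7 | 15 - s | 14 | 7 | 0 |
| 14 | 8 - s | 7 | 0 | 0 |
| 21 | 1 - s | 0 | 0 | 0 |

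For a patient starting at 25 mg, one level lower is 20 mg, so the maximum is 14 × 20 = 280 mg of lenalidomide. The schedule in 4.1 has hematology every 14 days in the first two cycles. Neutropenia found at the mid-cycle draw, about day 15, therefore makes no difference in this cycle.

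**5. When the removal line applies.** Four weeks from day s is day s + 28. The earliest value is 1 + 28 = 29, which is cycle 3. An omitted dose is skipped and the cycle schedule is kept (8.3, 8.5), so the cycle does not stretch. By then the table is a guideline.

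**The case against.** **On the ibrutinib start.** Section 7.12 is not exhaustive. It also leaves out the renal exception for lenalidomide that 7.11 states, yet the footnote to Table 8.32 applies that adjustment in phase II. One could say that 15.15(e) does the same for the liver. The difference is that the renal footnote expressly addresses the phase II dose. The hepatic text with dosing force, 8.51, is limited to impairment that develops on study, and 15.15(e) is drug information rather than a dosing instruction. It is also true that 15.15(e) reports no statistically significant effect of mild hepatic impairment as a covariate, and that few patients will have active, clinically significant impairment and still pass the 3.17 limits. Both points stand and keep the size of the concern down. They do not supply the missing instruction.

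A reader might infer that these patients would be overexposed or harmed, or that the response rate would be biased. The documents do not support that: the figures above are ratios of nominal doses, and neither exposure at these doses nor the number of such patients is given.

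**On neutropenia.** Waiting for Grade 1 satisfies all three lines at once, since Grade 1 also counts as ≤ Grade 2. A compliant path therefore exists, although it leaves the restart line with no work to do at Grade 2.

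A reader might infer that the row forces conflicting decisions to retain or remove patients in the binding cycle, or that the readings differ there by three full weeks of dosing. Steps 4 and 5 rule out both. A reader might also see a clash with the closing paragraph of 8.3. None is needed: a row may set a stricter removal limit than the general rule.

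**Conclusion.** The ibrutinib gap is real and should be closed. As written, a phase II patient with clinically significant class A impairment at entry starts at 1.5 to 3.0 times the protocol's own recommended dose if phase I selects 420 to 840 mg. There is no conflict if it selects 280 mg. This rests on reading 7.12 literally and on at least one such patient enrolling; the number is unknown and probably small.

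The neutropenia fault is minor. In the binding cycle only the restart line conflicts, for at most 14 dosing days and for none when omission starts on day 15 or later. The removal conflict arises only from cycle 3 on, under guideline status. How often Grade 4 neutropenia recovers only to Grade 2 is not given. These counts assume a 25 mg start, weekly counts and a patient who stays at Grade 2.

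Neither point bears on the sample size, the error rates or the primary analysis.

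**What to change.** **Ibrutinib.** Add one sentence to 7.12: patients whom the investigator judges to have clinically significant Child-Pugh A impairment at entry start ibrutinib at 280 mg/day. Tie it to that judgement and not to the class alone, for the reason given in step 2. The alternative is to exclude them in 3.29e2, as phase I does.

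The cost is lower ibrutinib exposure, or slightly narrower eligibility, for a few patients. The 280 mg start has a further cost. In Table 8.223 the first reduction from 280 mg is discontinuation, and under 8.1(d) permanent discontinuation of ibrutinib takes the patient off protocol therapy. The sponsor should either accept that or add a 140 mg step for these patients. Section 15.12 lists a 140 mg capsule, and 8.51 already uses that dose for class B impairment developing on study.

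**Lenalidomide.** Use one grade in all three lines of the Grade 4 neutropenia row. Changing the restart line to Grade 1 or better is the smallest edit and matches the reading that already satisfies every line; its cost is longer omission. Grade 2 throughout, as in the anemia row, is the alternative; its cost is restarting at lower counts. The choice is clinical and belongs to the sponsor.

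Both changes are amendment wording, with no change to the sample size or the analysis.
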